3. STUDY OBJECTIVES

The main objective of this study is to assess the health of multiple organs over a period of 6 to 9 months, using multiparametric abdominal MRI, in patients with type 2 diabetes who have been prescribed glucose lowering therapy (as per their standard of care).

Primary Objective	Primary Outcome Measure
1. To determine the degree of liver fibroinflammation in a large cohort of patients with type 2 diabetes, using multi-parametric abdominal MRI.	MRI metrics for liver fibroinflammation in patients with type 2 diabetes vs. the same metrics in healthy, non-diabetic individuals at baseline.
Secondary Objectives	Secondary Outcome Measures
1. To determine the degree of other liver abnormalities (such as fat infiltration) in a large cohort of patients with type 2 diabetes, using multi-parametric abdominal MRI.	1. Liver MRI metrics in patients with type 2 diabetes vs. the same metrics in healthy, non-diabetic individuals, at baseline for: 
 fat infiltration organ volume proportion of patients with evidence of non-alcoholic fatty liver disease (based on thresholds for liver fat or fibroinflammation).
2. To determine the degree of abnormality in other organs associated with type 2 diabetes and its	2. MRI metrics in patients in patients with type 2 diabetes vs. those in healthy, non-diabetic individuals, at baseline for:

comorbidities (pancreas, spleen, kidneys, aorta) using multi-parametric abdominal MRI
	
 organ volume, fat infiltration and fibroinflammation in abdominal organs affected by type 2 diabetes (spleen, pancreas, kidney) aortic health (aortic distensibility, diameter).

3. To assess whether multi-parametric abdominal MRI can quantify changes in multiple organs (liver, kidneys, pancreas, spleen and aorta) that occur over 6-9 months.
	
3. At 6-9 months: difference from baseline across the cohort in the following MRI metrics:
 
 organ volume, fat infiltration and fibroinflammation in abdominal organs affected by type 2 diabetes (liver, spleen, pancreas, kidney) aortic health (aortic distensibility, diameter) proportion of patients with evidence of non-alcoholic fatty liver disease (based on thresholds for liver fat or fibroinflammation).

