Visit 1 - Baseline, Day 0	0 weeks	
 ● Medical Hx ● Blood Tests ● Basic measurements (incl. height, weight, BMI, hip & waist circumference) ● Urine Sample ● Questionnaire
Visit 2	Within 35-days of Visit 1	
 ● MRI Scan ● BP (optional) ● ECHO (optional) ● Questionnaire
Visit 3	6-9 months	
 ● Medical Hx ● Blood Tests ● Basic measurements (incl. height, weight, BMI, BP) ● Urine Sample ● Questionnaire

Visit	Time	Visit Details
		
 ● MRI ● Medical Record Review

Further to this, participants will be asked to give consent to the review of their medical records at 3 time points - years 1, 3, and 5, following baseline assessment. This review will be conducted by authorised study investigators who will obtain clinical outcome measures relating to the study objectives, for example, measures of liver or kidney function.

In the majority of cases, follow-up data at years 1,3,5 will be entered from participants’ medical records. However, some participants may receive a short telephone call at years 1,3,5 to clarify any data which may be unclear or, to supply data which may be missing from their medical record. All participants recruited and scanned at Perspectum Ltd. in Oxford (a non-NHS clinical study site) will complete their years 1,3,5 follow-up medical history over the telephone: although all participants have consented to a medical records review during the study, medical records are not available to staff outwith the NHS. Thus self-reported data will be collected from these participants.

[figure not shown]

Figure 4 - Schematic of patient recruitment and study pathway (participants will be asked to confirm an absence of COVID-19 symptoms prior to each visit and may undergo a temperature measurement if necessary)

b. Study Setting

This is a multi-centre study conducted in 4 localities:

- 1) Liverpool
- 2) Oxford (Oxford University Hospitals NHS Foundation Trust - OUHNHSFT)

- 3) London (in the catchment of the Royal Free NHS Foundation Trust)
- 4) Oxford (Perspectum Ltd.)

Site 1) and 2) to recruit 50 T2D patients each, with the remaining 50 patients to be recruited between sites 3) and 4). Recruitment will be carried out from various settings to include community, primary care and secondary care diabetes clinics. Imaging will be carried out at local imaging centres for each locality.

5. Study Participants

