7.3.1. Standard study visit – assessments

Medical history (~10 min)

We will obtain a full medical history including age, diabetes presentation, diabetes complications, diabetes duration, previous and current diabetes medication, current medication regime, family history, smoking history, alcohol history, ethnicity, history of cardiovascular disease, QRISK score, history of kidney disease, history of liver disease and record of any other co-morbidities the patient may have.

We will confirm that the participant has no contraindications for MRI (e.g. pregnancy, pacemaker or other metallic unfixed implanted device, metallic fragments, extensive tattoos, severe claustrophobia, metal in clothing). A resting blood pressure measurement will be taken.

All measurements will be recorded on the study participant’s Case Report Form (CRF).

Anthropometric measurements (5 min)

We will measure the height and weight of the participant to calculate BMI and also take hip and waist circumference.

Blood sample (10 min)

Routine bloods will be performed as per standard-of-care for T2D or its complications and will include: HbA1c, serum creatinine, electrolytes, lipids, FBC (full blood count), LFT (liver function tests that include aspartate transaminase and alanine transaminase) and gamma glutamyl transferase (GGT). eGFR will also be calculated.

A further blood sample of approximately 10 ml will be taken to measure additional circulating biomarkers [such as the enhanced liver fibrosis test (ELF), N-terminal levels of type III procollagen (P3NP), pancreatic lipase, cystatin C, serum albumin, high sensitivity C-reactive protein, NT-proBNP and uric acid] and optional genetic testing for NAFLD or T2D associated genetic variants. Consent for genetic testing and to place blood samples in the biobank at Liverpool, Royal Free London or Oxford for future testing will be optional for all participants for up to 7 years after baseline to enable evaluation after full study completion.

Biomarker	Key organ(s)
HbA1c	Various/pancreas
Lipids	Various
GGT	Liver (various)

Full Blood Count	Various
LFT, including AST and ALT	Liver
Serum Creatinine	Kidney
Urine Albumin Creatinine Ratio	Kidney
Electrolytes	Kidney

Table 2 - Standard of care circulating biomarkers in study

Urine sample (10 min)

Routine urine sample collection will be performed as per standard of care to measure urine dipstick and urine albumin creatinine ratio.

MRI Scan (~30min)

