All participants will undergo a standardised imaging protocol (ATLAS) in an MRI scanner. At the time of initial consent, participants will be asked for their consent to have their images de-identified and stored. The MRI scan is not painful or risky, but a small minority of people feel claustrophobic. If this is apparent during screening, we will advise the patient to not participate. If this becomes apparent during a scan, we will stop the scan and take them out.

The MRI scans will be performed exclusively for research purposes and are not routinely looked at by a clinician. If a study investigator suspects an incidental finding, then they will follow the Perspectum Ltd incidental findings standard operating procedure (please refer to section 13.1 of this protocol). Blood pressure measurement may be taken at the same visit.

OPTIONAL Echocardiogram (~30min)

Participants may undergo a standardised transthoracic echocardiogram (ECHO) protocol using an ultrasound machine at visit 2. Participants will be asked for their consent to have de-identified images stored at the time of initial consent. The ECHO scans will be performed exclusively for research purposes and are not routinely looked at by a clinician. If a study investigator suspects an incidental finding, then they will follow the University of Liverpool incidental findings standard operating procedure.

Patient reported experience and outcome measures (~10min)

All participants will be asked to complete a questionnaire on a hand-held tablet at the end of all active study visits (or on their mobile phone/online). They will be asked to describe their experience within the clinical care setting and the impact of their prescribed treatment course.

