10.2. Analysis plan

Descriptive statistics will be used to summarise subject characteristics. Summary data will be calculated for MRI metric values (Table 3). Normality will be determined by use of the Shapiro-Wilk test. Results will be expressed as means with standard deviation (SD) for continuous variables and as numbers and percentages for categorical variables.

Analysis of variance will be used to test for differences between multiple groups.

The primary endpoint will be a comparison of MRI metric values for fibro-inflammation in the liver compared to a matched non-diabetic control group from the UK Biobank(30) or from other studies (31) (Table 3). This will be assessed with a two-sample, two-sided t-test. Secondary endpoints include a comparison of individual MRI metric values [summarised in table 3 below] in individual organ associated with T2D and its comorbidities [summarised in table 3 below] at baseline (visit 1/visit 2) compared to a matched non-diabetic control group from the UK Biobank or other studies. These will also be assessed with two sample, two-sided t-tests. Additionally, the prevalence of mean liver PDFF and / or mean liver cT1 above NAFLD thresholds in the study cohort will be compared to the matched non-diabetic control group, using a Chi-squared test.

MRI metric	Organ(s) or Location(s)	Associated organ characteristic
For primary endpoint		
cT1	Liver	Fibro-Inflammation
For secondary endpoints		
Diameter of Aorta	Heart	Local Blood Flow
Aortic Distensibility	Heart	Elasticity of Aorta
T1	Spleen, Kidney, Pancreas	Fibro-Inflammation
T2*	Spleen	Iron Level
PDFF	Liver, Spleen, Pancreas	Fat content
Volume	Liver, Spleen, Kidney, Pancreas	Size
Optional exploratory endpoint metrics		
T2* Gradient	Kidney	Oxygenation
D	Kidney	Glomerular Filtration
PDFF	Kidney	Fat Content

Volume of Visceral Adipose Tissue (VAT)	Abdomen	Fat Content
Abdominal Subcutaneous Adipose Tissue Volume (ASAT)	Abdomen	Fat Content
Skeletal Muscle Index	Abdomen	Muscle Content

Table 3 - MRI metrics in relevant organs

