Change from baseline in MRI metrics values at 6 to 9-months post-treatment will be assessed as secondary endpoints in each organ. These will be assessed with linear mixed effects model with an interaction variable of time. The change from baseline in proportion of patients at 6 to 9 months with mean PDFF and / or mean cT1 above NAFLD thresholds, across the whole study cohort, will be assessed using Chi-squared tests. Equivalent changes from baseline at 6 to 9 months will be assessed for HbA1c (glycaemic control), and other circulating biomarkers utilised in the clinical pathway for T2D, NASH and CKD [serum creatinine and eGFR (kidney), urine albumin creatinine ratio (kidney), lipids (NALFD), LFT (liver)], using linear mixed effects to assess changes over time. Odds ratios will be calculated by logistic regression analysis in relation to cardiovascular, liver, pancreatic and kidney-related events and or death, including hospital admissions, at 1, 3 and 5 years from baseline.

Exploratory endpoints will investigate the potential influence of glycaemic control/weight and of glucose/lowering therapies (oral/injectable agents) on prevalence of abnormality based on thresholds set from the healthy controls and on rate of progression for both biochemical and MRI-metrics, in subgroup analyses (including subgroups with abnormalities in multiple organs). Multiple testing will be corrected with Bonferroni correction. In addition, analysis of covariance will provide estimates of MRI metrics, adjusting for potential confounders such as baseline MRI metric, type of co-morbidity, type of therapeutic, HbA1c values, anthropometric measures and organ-specific circulating biomarker values as covariates. Similarly, additional associations of MRI metrics to biomarkers that are optional [for example left ventricular strain from the ECHO] or not in standard of care [for example pancreatic lipase] may be analysed, if evaluated locally or from stored, consented additional blood samples. Thresholds will be set based on Kaplan–Meier analysis to establish the proportions of patients in different MRI metric categories that remain free of diabetes-related events in the follow-up period. Differences between the curves will be compared using the log-rank test.

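### A blood pressure reading on the day of the baseline scan is not secured, although one is required at the follow-up scan visit, so aortic distensibility may not be measured alike at both times for some participants

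*Protocol*

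**What the plan says.** Section 3 lists "aortic health (aortic distensibility, diameter") under secondary outcome 2 (patients against healthy controls at baseline) and again under secondary outcome 3 (difference from baseline at 6-9 months). Table 3 in Section 10.2 places aortic distensibility among the secondary-endpoint metrics and describes it as "Elasticity of Aorta". Section 10.2 tests the metrics "at baseline (visit 1/visit 2) compared to a matched non-diabetic control group" and adds: "Change from baseline in MRI metrics values at 6 to 9-months post-treatment will be assessed as secondary endpoints in each organ". The change is modelled with linear mixed effects.

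MRI is done at Visits 2 and 3 (Sections 4 and 9, and Table 1 in Section 7.3). The blood pressure entries are:

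- **Visit 1, Section 4 visit table:** "Basic measurements (incl. height, weight, BMI, hip & waist circumference"). Blood pressure is not named.
- **Visit 2, Section 4 visit table:** MRI scan, with blood pressure marked as optional.
- **Visit 3, Section 4 visit table:** "Basic measurements (incl. height, weight, BMI, BP"), with MRI at the same visit and no optional marking.
- **Section 7.3.1, Medical history:** "A resting blood pressure measurement will be taken". Table 1 schedules the medical history at Visits 1 and 3, not at Visit 2.
- **Section 7.3.1, MRI Scan:** "Blood pressure measurement may be taken at the same visit". This sentence is permissive and names no visit.
- **Table 1:** no row for blood pressure.

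The window from Visit 1 to Visit 2 is 35 days in Section 4 and 21 days in Table 1. Section 4 lets the two visits share a day where patient and scanner availability allow.

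**The concern.** Distensibility is usually the relative change in aortic area over the cardiac cycle divided by pulse pressure. If that is how it is derived here, the blood pressure reading is part of the endpoint, and its timing relative to the scan matters.

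The plan secures a reading at the visit of the follow-up scan but not at the visit of the baseline scan. Some participants would have a baseline value built from a reading taken days or weeks before the images, and a follow-up value built from a same-visit reading. Others, whose Visits 1 and 2 coincide or whose optional reading was taken, would have matched values at both times. The change endpoint would then mix two measurement procedures, in proportions set by local scheduling and practice. An analysis plan can choose among the readings that exist, but it cannot supply one that was never taken.

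**Working it through.** **Step 1: which reading is required at each scan.** The protocol states no figure for this, so the entries are set side by side.

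| Scan | Reading at the scan visit | Required reading otherwise available |
|---|---|---|
| Baseline (Visit 2) | Optional (Section 4); permitted (Section 7.3.1, MRI Scan) | Visit 1 resting reading (Section 7.3.1, Medical history, with Table 1), up to 35 or 21 days earlier |
| Follow-up (Visit 3) | Listed without an optional marking (Section 4); required with the medical history (Section 7.3.1 with Table 1) | Not needed |

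A baseline reading exists for every participant who follows the protocol. What is not assured is that it was taken on the day of the baseline scan.

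**Step 2: effect on one person's value.** Assumptions, none of them from the protocol: distensibility D = relative area change / PP, where PP is pulse pressure; PP at the scan is 50 or 60 mmHg; the reading used differs from it by 5 or 10 mmHg.

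Relative error in D = PP at scan / PP used - 1.

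| PP at scan | Used 10 lower | Used 5 lower | Used 5 higher | Used 10 higher |
|---|---|---|---|---|
| 50 | 50/40 - 1 = +25.0% | 50/45 - 1 = +11.1% | 50/55 - 1 = -9.1% | 50/60 - 1 = -16.7% |
| 60 | 60/50 - 1 = +20.0% | 60/55 - 1 = +9.1% | 60/65 - 1 = -7.7% | 60/70 - 1 = -14.3% |

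**Step 3: effect on the cohort.** The endpoints are group means and mean change, so individual errors partly cancel. Suppose the PP used varies at random around the PP at the scan, with an assumed within-person SD. A simulation of 1,000,000 normal draws per setting, with PP cut off below at 20 mmHg, gave:

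| PP at scan | SD | Shift in mean D | Added CV of D |
|---|---|---|---|
| 50 | 5 | +1.0% | 10.4% |
| 50 | 8 | +2.8% | 18.0% |
| 50 | 12 | +6.7% | 30.7% |
| 60 | 5 | +0.7% | 8.6% |
| 60 | 8 | +1.9% | 14.4% |
| 60 | 12 | +4.6% | 24.3% |

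The main effect is noise. The small upward shift arises because the reciprocal is convex. To second order it is (SD/PP)²: for example (5/50)² = 1.0% and (8/50)² = 2.6%, close to the simulated 1.0% and 2.8%.

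**Step 4: when the mean change is biased appreciably.** Let f be the fraction of participants whose baseline value relies on a Visit 1 reading from another day. If blood pressure differs systematically between Visit 1 and the scan day, the error in the baseline mean is about f times the matching error in Step 2, and it passes into the change with the opposite sign. The protocol gives no basis for f or for such a difference, so no figure can be put on this bias.

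**The case against.** The strongest reply is that the text permits matched measurement. Blood pressure may be taken at Visit 2, Visits 1 and 2 may share a day, and in either case baseline and follow-up are alike. This stands, and it limits the point to some participants. A reader might infer that all 150 baseline values are affected; that is only a ceiling, because nothing shows how often the reading is skipped or the visits are separate.

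A reader might also infer that participants without a Visit 2 reading lose the endpoint, or that there is no baseline blood pressure at all. The documents do not support that. Section 7.3.1 with Table 1 requires a resting reading at Visit 1. Its absence from the Section 4 list for that visit is a gap between summary and detail, and that list is introduced as non-exhaustive.

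The protocol gives no formula for distensibility and never says that blood pressure enters it. The ATLAS imaging procedure is not shown and may define both the derivation and the reading to use. This also stands: the consequence is conditional on the usual definition. The uneven blood pressure entries do not depend on it.

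It is tempting to read the -17% to +25% as bias in the endpoint. It is the error for one person under assumed inputs. It is equally tempting to suppose that a treatment change between Visits 1 and 2 shifts blood pressure. Section 4 aims at newly prescribed and intensifying patients, so a change is possible, but Section 5.1 requires that participants already take glucose-lowering therapy. No text places a change in that interval or gives an effect on blood pressure.

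**Conclusion.** The point holds in limited form. A reading on the day of the baseline scan is not secured, while one at the follow-up scan visit is, so for some participants the two distensibility values may not be measured alike.

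The size is conditional. With a pulse-pressure definition and an assumed 50 mmHg, a mismatch of 5-10 mmHg changes an individual's baseline value by between -17% and +25%. Across the cohort this is mainly extra noise at baseline, with a shift in the mean of about 1-7% under assumed within-person SDs of 5-12 mmHg if everyone relied on a mismatched reading. A larger bias in mean change needs a systematic difference between Visits 1 and 2, which the documents neither show nor exclude.

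Only distensibility, one of many secondary metrics, is concerned. Liver cT1 and aortic diameter do not depend on blood pressure. The point is worth acting on because the remedy is cheap and a missing reading cannot be recovered later.

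**What to change.** 1. Make the blood pressure reading already listed at Visit 2 a required measurement, taken in the same session as the MRI at both Visit 2 and Visit 3.
2. State how distensibility is calculated and, if blood pressure enters it, that the same-session reading is the one used.
3. Reconcile the blood pressure entries in the Section 4 visit table, Table 1 in Section 7.3, and the Medical history and MRI Scan paragraphs of Section 7.3.1. The 35-day and 21-day windows for Visit 2 are a separate inconsistency that also needs reconciling.
4. For participants already scanned without a same-day reading, record the date of the reading used, so that a sensitivity analysis can set them apart.

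The cost is a few extra minutes with a cuff at the visit, plus small edits to the visit table and case report form. It adds no visit.

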7.3.2. Outcome data collection

Participants will be asked to give written consent to allow the study team to access their primary care and hospital medical records. Data will be collected to assess outcome data pertaining to cardiovascular, kidney, liver and diabetes related clinical events, as well as any further complications and hospital admissions. Primary care medical records will be reviewed at 1, 3 and 5-year timepoints following the baseline visit. In the majority of cases, follow-up data at years

1,3 and 5 will be entered from participants' medical records. However, some participants may receive a short telephone call to clarify any data which may be unclear or, to supply data which may be missing, from their medical record. All participants recruited and scanned at Perspectum Ltd. in Oxford (an approved non-NHS clinical study site) will complete their years 1, 3 and 5 follow-up medical history over the telephone: although all participants have consented to a medical records review during the study, medical records are not available to staff outwith the NHS. Thus self-reported data will be collected from these participants.

7.3.3. Withdrawing from the study

Each participant has the right to withdraw from the study at any time. In addition, the Investigator may discontinue a participant from the study at any time if they deem it necessary for reasons that might include:

- Ineligibility (arising during the study)
- Significant protocol deviation
- Significant non-compliance with study requirements
- Withdrawal of consent
- Loss to follow up

Data already collected from the study participants will be included in the analysis. Withdrawn participants will be replaced. The reason for withdrawal (if provided) will be recorded in the CRF.

8. DEFINITION OF END OF STUDY

The end of the study will be the date that 5-year outcome data is obtained on the last recruited study participant. Active participation will end when the last recruited participant attends their 6 to 9 month visit (Visit 3).

